3.2 Safety Variables

The safety of acalabrutinib in subjects with COVID-19 when administered with BSC is a primary endpoint and will be assessed by type, frequency, severity, and relationship to study treatment of any treatment-emergent adverse events (TEAEs) or abnormalities of laboratory tests, serious adverse events (SAEs), or adverse events leading to discontinuation of study treatment.

3.2.1 Adverse events

After the signing of the ICF, all SAEs must be reported. After the first dose of study treatment, all AEs/SAEs, irrespective of attribution of causality, must be reported. AE reporting, irrespective of seriousness, ends 28 (\pm 3) days after the last dose of study treatments.

Events will be defined as treatment-emergent if they onset, or worsen (by investigator report of a change in intensity), during the treatment period as defined in the CSP. The Medical Dictionary for Regulatory Activities (MedDRA) (using the latest or current MedDRA version) will be used to code the AEs. AEs will be graded according to the National Cancer Institute Common Terminology Criteria for AEs (CTCAE) version 5.0. For events with varying severity, the worst reported grade will be used.

Missing start and stop dates for AEs will be handled using the rules described in Section 4.1.

3.2.2 Exposure, dose intensity and treatment compliance

Study drug exposure and dosing information will be collected for acalabrutinib-treated subjects. The intended and actual treatment duration [days], the average daily dose (mg), relative dose intensity (%) and treatment compliance (%) will be reported according to table 5.

By subject exposure listing will be provided.

Table 5 Definition of Exposure Variables

Parameters	Definition	
Intended treatment duration	Date of last dose (> 0mg) - date of first dose + 1	
Actual treatment duration	Intended treatment duration (days) – total duration of interruptions (days)	
Average daily dose	total dose received (mg) / Actual treatment duration (days)	
Relative dose intensity[RDI]	$100\% \times d/D$ where	
	d is the actual cumulative dose [mg] delivered up to the actual last day of dosing for the drug, and	
	D is the total dose of the drug that would be delivered: Actual treatment duration [days] \times 100 [mg] \times 2	
Treatment compliance	$100 \times [1$ - (total number of days of study drug interruption / actual treatment duration)].	

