1.2 Study Design

Approximately 20 participants will be included to ensure at least 16 participants are evaluable. participants will receive acalabrutinib suspension (ie, acalabrutinib 100 mg suspension in COCA-COLA® delivered via NG tube) bid for 14 days (a maximum of 28 doses). In addition to receiving best supportive care (SOC).

To assess the effect of PPIs, all participants must be receiving treatment with a PPI at the start of the study. Treatment with a PPI can begin at any time prior to enrollment, provided participants have received PPI treatment for at least 24 hours prior to the first dose of acalabrutinib suspension. Any PPI is permitted, provided it meets the minimum equivalent daily dose of 20 mg rabeprazole. Participants must be on this dosage of PPI at the start of the study. They may be weaned off PPIs during the study if medically appropriate.

[figure not shown]
Blood samples for plasma PK assessment of acalabrutinib and its metabolite (ACP-5862) will be collected at pre-dose and 0.5, 1, 2, 4, 6, and 12 hours following treatment with acalabrutinib suspension as described in the table below. Note that the sample at 12 hours must be collected prior to the subsequent acalabrutinib dose (for trough PK sample).

Table 2 PK Visit and Description

PK Visit	Description	Rationale
PK Visit 1	First PK sampling will occur on Day 1 (ie, first dosing day for acalabrutinib suspension)	Allows an early assessment of acalabrutinib and ACP-5862 PK in participants receiving acalabrutinib suspension via NG tube
PK Visit 2	Second PK sampling will occur a minimum of 4 days after the start of PPI treatment, irrespective of the timing of NG tube placement and any time after 2 doses of acalabrutinib suspension have been given (ie, PK sampling can begin prior to the third dose, or anytime thereafter) PK Visit 2 can occur as early as Day 2 (if participant has been on a PPI for ≥ 4 consecutive days prior to receiving the third acalabrutinib dose), and up to Day 4 (if participant initiated PPI treatment 24 hours prior to receiving the first dose of acalabrutinib on Day 1)	PPI exposure must occur for 4 consecutive days to reach the maximum PPI on-target effect PK sample can commence at any point after the second dose of acalabrutinib suspension to ensure steady-state levels of the active metabolite and

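### Table 5 counts whole calendar dates for a twice-daily drug, so RDI and average daily dose fall below 100% and 200 mg when a course begins or ends on a one-dose date, even with no dose missed

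*SAP*

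**What the plan says.** SAP Section 1.2 sets each administration at 100 mg through the NG tube and the schedule as "bid for 14 days (a maximum of 28 doses"). The course is thus fixed both in days and in doses.

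Section 3.2.2, Table 5, measures exposure in calendar dates:

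- The starting point, which the table labels intended duration, is a difference of dates: "Date of last dose (> 0mg) - date of first dose + 1".
- Days of interruption are then taken off, which leaves what the table calls the actual duration.
- That day count is the divisor that turns milligrams received into an average per day.
- RDI is the percentage ratio of the cumulative milligrams given, d, to an expected total, D. The expected total starts from the same day count, in these words: "D is the total dose of the drug that would be delivered: Actual treatment duration [days"]. Each of those days is then charged two doses of 100 mg.

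Nothing in the SAP says how to treat a first or last date on which only one dose was due. Section 1.2 identifies Day 1 as the first dosing day but gives no clock time for the first dose. Section 4.5.2 plans summaries of RDI (including its minimum and maximum) and of average daily dose from these definitions.

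**The concern.** The numerator of RDI counts milligrams actually given. The denominator charges two doses to every date touched by the course. The two agree only when the first dose is the first of its day and the last dose is the second of its day. Otherwise the denominator includes a dose that was never scheduled between the first and last administration, and the ratio falls for a reason unrelated to missed doses. Average daily dose uses the same day count and inherits the same shortfall.

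At stake is how the planned exposure tables read. Enrolment is about 20 (Section 1.3). The SAP foresees discharge before Day 14 (visit windows in Section 4.1) and premature discontinuation of treatment (Section 4.2.1), so short courses are plausible. The shortfall is largest in those courses, and a single one can set the reported minimum.

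**Working it through.** **Inputs.** Unit dose 100 mg, twice daily, 14 days, at most 28 doses (Section 1.2). Duration, average daily dose and RDI as defined in Table 5 (Section 3.2.2). Interruption days are zero throughout, so actual duration equals the date count n.

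**The plan's own figure.** 14 days × 2 = 28 doses, or 28 × 100 = 2800 mg. Table 5 gives D = 14 × 100 × 2 = 2800 mg, so RDI = 2800/2800 = 100% and average daily dose = 2800/14 = 200 mg. The definitions agree with the design when the course starts in the morning and ends in the evening.

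**General form, 12-hourly dosing with none missed.**

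- RDI = 100 × (doses × 100)/(n × 200); average daily dose = doses × 100/n.
- One half-day, at either end: doses = 2n − 1, so RDI = 100 × (2n − 1)/(2n).
- Half-days at both ends: doses = 2n − 2, so RDI = 100 × (n − 1)/n.

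**Results.**

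| Uninterrupted course | Doses | Dates | Given / D (mg) | RDI | Average daily dose |
|---|---|---|---|---|---|
| Morning start, evening stop | 28 | 14 | 2800/2800 | 100% | 200 mg |
| One half-day at either end | 27 | 14 | 2700/2800 | 96.4% | 192.9 mg |
| Evening start, all 28 doses | 28 | 15 | 2800/3000 | 93.3% | 186.7 mg |
| Evening start, morning stop | 14 | 8 | 1400/1600 | 87.5% | 175 mg |
| Morning start, stop after third morning dose | 5 | 3 | 500/600 | 83.3% | 166.7 mg |
| Evening start, morning stop | 4 | 3 | 400/600 | 66.7% | 133.3 mg |
| Single dose | 1 | 1 | 100/200 | 50% | 100 mg |

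The 5-dose and single-dose rows do not need an evening start.

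**Effect on a summary.** If one of 20 subjects had RDI 50% for this reason and the other 19 had 100%, the mean would fall by 50/20 = 2.5 points and the minimum would read 50%.

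**After correction.** With D = 100 mg × doses scheduled from first to last administration, every row gives 100%. Dividing total mg by scheduled doses/2 gives 200 mg. For example, with 5 doses: 500/500 = 100% and 500/2.5 = 200 mg.

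**Secondary check, compliance.** Table 5 bases compliance on interruption days without defining an interruption. Take a subject given one of two doses on each of 14 dates, 14 of 28 doses in all.

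- If only whole days count, interruption is 0: compliance = 100 × (1 − 0/14) = 100%, and RDI = 1400/2800 = 50%.
- If each missed dose counts as half a day, interruption is 14 × 0.5 = 7 days and actual duration is 14 − 7 = 7: RDI = 1400/1400 = 100%, and compliance = 100 × (1 − 7/7) = 0%.

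Both results depend on a rule that the SAP does not state.

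**The case against.** The strongest reply is that whole-day duration is a rounding convention, not a mistake. A subject who stops after a morning dose did not receive that day's second dose, and charging 200 mg to each treated date is a coherent choice. That is fair as a description of the convention. It does not fit well with a denominator described as the dose that would be delivered, since that figure can exceed the design maximum. Nor does it suit a course of only 14 days, where half a day is not negligible.

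Several stronger readings are tempting and are not supported:

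- *That the first dose can fall at any hour.* The SAP gives only a minimum PPI period before dosing and no clock time. The protocol, not at hand, may fix dose times. That could remove the evening-start cases, but not a stop after a morning dose.
- *That 93.3% is the typical error.* It requires dosing into a 15th date. If 14 days means calendar days, a late start yields 27 doses and 96.4%.
- *That subjects would be classed as under-dosed.* The SAP sets no RDI or compliance threshold and classifies nobody.
- *That missed doses would be hidden.* On the whole-day reading, RDI shows 50% for a subject missing one dose every day. A by-subject exposure listing and a tabulation of interruptions are also planned.
- *That compliance is necessarily 100% for such a subject.* This holds only if interruptions are counted in whole days.
- *That a primary result is affected.* No PK parameter or adverse-event definition uses these quantities, and deliverability by NG tube is not a stated endpoint.

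**Conclusion.** The point holds as an edge effect in the exposure definitions. With no dose missed between first and last administration, Table 5 gives RDI below 100% and average daily dose below 200 mg whenever the first or last date carries only one dose of the course. The loss is 3.6 points for 27 doses over 14 dates, or 6.7 points if 28 doses run over 15 dates. It rises to 16.7 points for 5 doses over 3 dates and 50 points for a single dose.

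This rests on regular 12-hourly dosing, zero interruption days and the absence of a protocol rule for one-dose dates. How many subjects would be affected cannot be judged from the SAP. The consequence is limited to descriptive summaries of exposure. The change is worth making because these summaries accompany the safety analysis, short courses are plausible in a small hospitalised sample, and the remedy is cheap.

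**What to change.** In Table 5, set D = 100 mg × the number of doses scheduled from the first to the last administered dose, at most 28. Use scheduled doses/2 as the divisor for average daily dose. Alternatively, keep the date count but charge half a day for a first or last date with only one scheduled dose. For an uninterrupted course the two are equivalent. Where there are interruptions, the SAP should say whether doses falling within them stay in the count, because Table 5 at present subtracts interruption days.

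Also state whether a single missed dose adds to interruption days. If compliance is instead redefined as doses given over doses scheduled, it will equal RDI whenever every dose is 100 mg, so one of the two would then be redundant.

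The cost is a wording change in one table and a short programming change. It needs dose times, or at least an AM/PM marker, for the first and last dose. The SAP says only that dosing information is collected, so the sponsor should confirm that these are recorded.

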4.5.2 Exposure, dose intensity and treatment compliance

Study drug exposure will be listed and summarized for acalabrutinib-treated subjects in the SAF. The following summaries will be produced using the definition of exposure variables in Table 5 in Section 3.2.3:

- Intended treatment duration
- Actual treatment duration
- Summary statistics (n, mean, median, SD, minimum, and maximum) of RDI
- The number and percentage of dose interruptions, dose increases, and reasons for dose interruptions and dose increases
- Calculated average daily dose
- Treatment compliance

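### SAP Table 5 divides interruption days by a duration that already excludes them, so treatment compliance is too low after any interruption and can fall below zero

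*SAP*

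**What the plan says.** Section 3.2.2 of the SAP (Table 5) builds the exposure variables in a chain.

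- Intended treatment duration is "Date of last dose (> 0mg) - date of first dose + 1". Despite its name, this is the observed span from first to last non-zero dose.
- Actual treatment duration is "Intended treatment duration (days) – total duration of interruptions (days").
- Average daily dose is "total dose received (mg) / Actual treatment duration (days").
- In RDI, the numerator is defined by "d is the actual cumulative dose [mg] delivered up to the actual last day of dosing for the drug". The denominator is defined by "D is the total dose of the drug that would be delivered: Actual treatment duration [days"], multiplied by 100 mg and by 2.
- Treatment compliance is 100 times one minus "total number of days of study drug interruption / actual treatment duration".

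Section 4.5.2 then reports intended and actual duration, "Summary statistics (n, mean, median, SD, minimum, and maximum) of RDI", average daily dose, treatment compliance, and the number, percentage and reasons of dose interruptions. Nothing in the SAP gives compliance a different denominator or a lower limit of zero.

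**The concern.** Compliance is meant to be the share of days on which treatment was not interrupted. For that, the denominator must be the whole span in which interruptions could occur. Table 5 instead uses the days left after interruptions are removed. The ratio is then interrupted days to treated days, which is not a proportion and can exceed 1. The resulting percentage is too low for every subject with an interruption, and has no meaning once interrupted days outnumber treated days.

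RDI uses the same reduced duration, with a different effect. Whole interrupted days drop out of both the delivered dose and the reference dose, so they leave RDI unchanged.

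What is at stake is the exposure table in the study report. With about 20 participants, one or two impossible or heavily understated values would show in the minimum and the mean.

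**Working it through.** **Inputs.** Table 5 gives T = intended duration, I = interruption days and A = T − I. The example uses T = 14, from the regimen in section 1.2 ("bid for 14 days (a maximum of 28 doses"). The SAP states no expected interruption rate and no compliance or RDI value, so there is no plan figure to reproduce. I is an assumption and is varied. For T = 14 it cannot exceed 12, because the first and last days are dosing days.

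**Compliance as written.** 100 × [1 − I/A] = 100 × [1 − I/(T − I)].

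**Compliance on the full span.** 100 × [1 − I/T].

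**Shortfall.** 100 × [I/(T − I) − I/T] = 100 × I²/[T(T − I)]. This is positive for every I > 0.

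| I | A | As written | On T | Shortfall (points) |
|---|---|---|---|---|
| 0 | 14 | 100.0% | 100.0% | 0 |
| 1 | 13 | 92.3% | 92.9% | 0.5 |
| 2 | 12 | 83.3% | 85.7% | 2.4 |
| 4 | 10 | 60.0% | 71.4% | 11.4 |
| 7 | 7 | 0.0% | 50.0% | 50.0 |
| 8 | 6 | −33.3% | 42.9% | 76.2 |

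The written formula reaches zero at I = T/2 and is negative beyond it. The same happens for shorter spans: T = 7 with I = 4 gives 100 × (1 − 4/3) = −33.3%, and T = 10 with I = 6 gives 100 × (1 − 6/4) = −50%.

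**Effect on a mean.** In 20 subjects, one subject with T = 14 and I = 4 lowers mean compliance by 11.4/20 = 0.6 points. One subject with I = 8 lowers it by 76.2/20 = 3.8 points and makes the minimum negative.

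**RDI as written.** RDI = 100 × d/(A × 200 mg). Average daily dose is d/A, so RDI = 100 × (average daily dose)/200 mg exactly. The two rows carry the same information.

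- T = 14, I = 4, full dosing on the other 10 days: d = 2000 mg and RDI = 2000/2000 = 100%. On intended duration it is 2000/2800 = 71.4%.
- Same subject with two further single doses missed: d = 1800 mg and RDI = 1800/2000 = 90%. RDI as written therefore still responds to missed single doses.

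**A cap at 28 doses in D.** Take 28 doses over a 20-day span with 6 interrupted days. Capped RDI is 2800/2800 = 100%, while compliance on T is 1 − 6/20 = 70%. Uncapped RDI on T is 2800/4000 = 70%. The cap would bring back the insensitivity to interruptions.

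**The case against.** The case for leaving Table 5 alone has several parts, and much of it stands.

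- **The consequences are narrow.** The safety endpoint in section 3.2 is assessed through adverse events and laboratory abnormalities. No analysis set, PK parameter or efficacy variable uses compliance or RDI. This stands and sets the severity.
- **Interruptions remain visible.** Section 4.5.2 reports interruptions with reasons and both durations, and section 3.2.2 promises a by-subject exposure listing. A subject's correct compliance can be recovered as actual divided by intended duration. This is true, but it does not make the summarised compliance row correct.
- **Large errors need long interruptions followed by resumption.** The span ends at the last non-zero dose, so a hold that becomes permanent is not counted. At one or two days out of 14 the error is 0.5 to 2.4 points. This stands as to size. The formula is still wrong for every interruption.
- **RDI over days on treatment is a legitimate measure.** It detects reduced and missed single doses, and interruptions do not push it out of range. This stands too. A reader might infer that RDI contains the same arithmetic error as compliance, or that RDI at 100% beside lower compliance is a contradiction. Neither follows: once compliance is corrected, 100% RDI with 71.4% compliance means full dosing when dosed, with 4 of 14 days interrupted. What remains is that the description of D does not fit its formula and that RDI duplicates average daily dose.

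A reader might also expect the error to distort an exposure-response analysis. The only such text is an optional statement within the PK analysis (section 4.3), where exposure most naturally means PK exposure. It mentions neither RDI nor compliance.

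**Conclusion.** The compliance formula is wrong as written, and this follows from Table 5 alone. For a 14-day span it understates compliance by 2.4 points at 2 interrupted days and 11.4 points at 4. It gives 0% at 7 days and −33.3% at 8. The sizes rest on the assumed span and interruption counts. The direction of the error does not.

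The RDI point is secondary. It is a choice of definition that is poorly described and adds nothing to average daily dose, not an arithmetic error. The 100% example assumes full dosing on every non-interrupted day.

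Since safety is a primary objective, a reader might take this for a critical fault. The SAP does not support that, because the affected variables appear only in descriptive exposure summaries. It should be fixed before those tables are programmed. Neither measure shows early permanent stopping, since intended duration is the observed span. The correction below does not change that.

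**What to change.** In Table 5, redefine treatment compliance as 100 × [1 − interruption days / intended treatment duration]. It then stays between 0 and 100%.

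For RDI, choose one option and state it:

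- use intended treatment duration × 100 mg × 2 as D, without a 28-dose cap, so that whole-day interruptions lower RDI; or
- keep the formula, label it as dose intensity over days on treatment, and reword the description of D to match.

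The cost is one denominator for compliance, and one denominator or one label for RDI, in Table 5 and the derivation program. No new data are needed.

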3.2.3 Laboratory assessments

Laboratory tests will be performed as specified in the SoA in the CSP.

For the derivation of baseline and post-baseline visit values, the rules described in Section 4.1 considering definition of baseline, and how to handle multiple records will be used.

Change or percentage change from baseline in hematology and clinical chemistry variables, as well as ferritin and CRP will be calculated for each post-baseline assessment recorded in the eCRF.

Laboratory abnormalities will be defined based on laboratory normal ranges (universal normal ranges for central laboratory tests), and absolute values will be classified as low (below range), normal (within range or limits of range), or high (above range).

Laboratory parameters will also be classified using the National Cancer Institute Common Terminology Criteria (CTC) version 5.0 into CTC grades.

The denominator used in laboratory abnormality summaries will include only evaluable subjects (i.e., those who had sufficient data to have the possibility of an abnormality). Physical examinations and chest imaging, electrocardiograms and echocardiograms

3.2.4 Physical examination and chest imaging, electrocardiograms and echocardiograms

Physical examinations and chest imaging, electrocardiograms and echocardiograms will be performed as per SoA.

A 12-lead electrocardiogram (ECG) will be done at screening, as clinically indicated, Day 14 or discharge. Baseline is defined, after taking the average of the triplicates, as the latest non-missing averaged triplicate prior to the first study drug.

The left ventricular ejection fraction (LVEF) will be reported when echocardiograms (ECHO) are conducted. The LVEF % will also be reported.

Abnormalities recorded at screening or baseline for ECG or ECHO results will be recorded as a concurrent condition. Abnormalities first recorded during the treatment period will be recorded as AEs unless unequivocally related to the disease under study.

3.2.5 Vital signs and arterial blood gases

The vital signs to be collected are blood pressure, respiratory rate, oximetry, pulse, and body temperature, as per the SoA in the CSP.

The oxygen-haemoglobin saturation of the blood will be assessed using standard pulse oximetry or by arterial blood gas for those subjects who have an arterial blood gas obtained.

The vital sign and blood oxygen measurements are: systolic BP (mmHg), diastolic BP (mmHg), MAP (mmHg), pulse rate (bpm), respiratory rate (breaths/min), body temperature and blood oxygen-haemoglobin saturation (%). MAP will be calculated as:

diastolic BP + 1/3 (systolic BP- diastolic BP).

If multiple vital sign measurements are taken per day, the measurement closest to 08:00 each day will be used. Vital sign measurements taken at unscheduled visits will not be used in the summaries of vital signs. However, any vital sign measurements taken at unscheduled visits that are regarded as abnormal or clinically significant will be presented as such.

